4 STUDY POPULATION

4.1 Number of participants

A total of 224 patients (112 in each arm) will to be recruited from approximately 20 UK sites over a 24-month period.

4.2 Inclusion criterion

Patient <60 years with symptomatic medial compartment knee OA who the treating orthopaedic surgeon considers a suitable candidate for medial opening wedge HTO

4.3 Exclusion criterion

1. Age <18 years or >60 years
2. Body mass index (BMI) >40
3. Patients considered for HTO but who DO NOT have any knee OA including:
 - a. Offloading HTO for concomitant cartilage repair (No OA)
 - b. Offloading HTO solely to treat ligamentous instability (ACL/PCL)
 - c. Symptomatic avascular necrosis/osteonecrosis
 - d. Correction of intraarticular or extraarticular post-traumatic knee deformity
4. Patients requiring double-level knee osteotomy for correction of deformity
5. History of inflammatory arthropathy including rheumatoid arthritis, ankylosing spondylitis, gouty arthropathy and psoriatic arthropathy
6. Previous high tibial or distal femoral osteotomy in same or contralateral knee
7. Previous knee replacement (partial or total) in the same or contralateral knee
8. Cognitive impairment resulting in the inability to consent.
9. Inability to comply with study procedures.
10. Previous history of septic arthritis in the knee

4.4 Co-enrolment

Should the need for co-enrolment arise, the sponsor policy in relation to co-enrolment will be followed . This can be viewed at the following website link:

www.accord.scot/sites/default/files/POL008%20Co-enrolment%20v2.0%20-%20signed.pdf

5 PARTICIPANT SELECTION AND ENROLMENT

5.1 Identifying participants

Potential patients will be identified and approached in outpatient or specialist knee clinics by the usual care team comprising the participating surgeon or their delegated specialist trainee. Patients will be provided with the MOTION Patient Information Sheet & Consent Form (PISCF) (Appendix 1) and asked if they are willing to be contacted by the local research team using a 'MOTION Consent to contact' form (Appendix 2). If so a screening visit to assess their eligibility for the study will be arranged. If the patient is identified during an outpatient appointment this screening visit could coincide with their outpatient clinic appointment, depending on local circumstances.

5.2 Consenting participants

Participants meeting the inclusion and exclusion criteria will be approached for consent by a member of the research team delegated to take consent allowing sufficient additional time to consider the study information. Following consent, data will be collected to allow randomisation. The trial consent form is detailed in Appendix 1.

There is provision within the trial consent form to request patient consent for longer term follow-up at 5 and 10- years post-intervention through data linkage, to measure survivorship of HTO and later requirement for knee replacement.

This will be a separate study and additional funding to conduct the study will need be sought.

The trial also incorporates a process evaluation (please refer to section 9.4 for details). As part of the initial consent to be contacted (Appendix 2), patients and delivery staff will be asked for their consent to be contacted by the process evaluation team. A subgroup of patients and delivery staff (including patients who agree to participate in the MOTION study and those who don't) will be asked to consent (using a separate process evaluation consent form and information sheet) to a brief interview by the process evaluation team to explore their decision making.

5.3 Withdrawal of participants

Participants are free to withdraw from the study at any point or a participant can be withdrawn by the investigator. If withdrawal occurs, the primary reason for withdrawal will be documented in the participant's case report form. The participant will have the option of withdrawal from all aspects of the trial but continued use of data collected up to that point. To safeguard rights, minimum personally identifiable information will be collected, and a withdrawal form completed. The trial management and trial steering committee will monitor these withdrawals from the trial. The process evaluation team will also be informed of any patient who previously gave permission for re-contact but has since withdrawn for the study.

6 STUDY ASSESSMENTS

Participant Follow-up at 12 and 24 months

All available methods of communication will be used for the study assessments including email, post, telephone and NHS approved video links (e.g. NearMe), with a maximum of two reminders sent where required. The preferred method for collection of baseline data will be with a face-face consultation. Where local circumstances prevent this, baseline data may also be collected by telephone or video link. After collection of the baseline data, follow up will occur at two further intervals - 12 and 24 months post-randomisation, with all study assessments at these time points undertaken remotely via email, post or telephone.

Minimum requirements/acceptable variations (MRAV) proforma

A standardised minimum requirements/acceptable variations (MRAV) proforma will be completed for each participant approximately 6 months post intervention to record the fidelity of the trial interventions. This proforma will be completed by the local research team at each participating centre. It should be noted that this proforma is collected from approximately 6 months post-intervention, and this interval may be different from the time period since randomisation due to NHS waiting lists. In the Personalises Knee Therapy (PKT) group, data will be collected and recorded at each one-to-one session. The date of the last one-to-one physiotherapy session (usually the 6th session) will be considered as the date for completion of the intervention.

Table 2: Tabulated summary of assessments						
ASSESSMENT	Screening	Baseline	6-month MRAV proforma (HTO)	6-month MRAV proforma (PKT)	12-month PROMS	24-month PROMS
Who is responsible for assessment?	Local site team	Local site team	Local site team	Local site team	ECTU	ECTU
Allowed variation in months			±6	±6	±3	±3
How is assessment done?	Clinic review and/or Medical records review	Clinic review	Medical records review	Patient attendance at 6 supervised physiotherapy sessions Medical records review Patient exercise diary review	Email and/or Post and /or Online portal	Email and/or Post and /or Online portal
Assessment of eligibility criterion	X	X				
Log of eligible patients excluded (declined, exclusion criterion, other reason)		X				
Written Informed consent		X				
Baseline data & demographics		X				
Randomisation		X				
Minimum requirement/acceptable variation (MRAV) proforma			X	X		
Primary outcome score – KOOS		X			X	X
Oxford Knee Score (OKS)		X			X	X
Forgotten Joint Score (FJS)		X			X	X

EuroQoL score (EQ-5D-5L)		X			X	X
Pittsburgh Sleep Problem Scale		X			X	X
Return to Work/Employment questionnaire		X			X	X
Additional operative intervention in study knee					X	X
Complications					X	X

(MRAV- minimum requirements/acceptable variations proforma; PROMS – Patient reported outcome measures; ECTU – Edinburgh Clinical Trials Unit)

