2.2 ENDPOINTS

The primary and secondary endpoints will be captured within the following framework: **Population** - NHS patients <60 years with symptomatic knee OA localised to the medial compartment in whom surgical intervention is indicated. **Intervention** - Surgery with medial opening wedge HTO followed by standard postoperative rehabilitation based on local pathways. **Comparator** - Non-surgical intervention with Personalised Knee Therapy (PKT) delivered within an NHS physiotherapy department.

Primary endpoint

The primary outcome is the composite 24-month Knee Injury and Osteoarthritis Outcome Score (KOOS) score (www.koos.nu).

Secondary endpoints

1. Minimum requirements/acceptable variation (MRAV) proforma completed between 6 -12 months post intervention (note that this interval may be different from the same period post-randomisation due to NHS waiting lists)
2. KOOS composite score 12 months post-randomisation.
3. Five separate KOOS subscales at 12 and 24-months post randomisation.
4. Oxford Knee score (OKS, www.innovation.ox.ac.uk) at 12 and 24- months post-randomisation (46).
5. Forgotten Joint Score-12 (FJS-12, www.forgotten-joint-score.info) at 12 and 24-months post-randomisation (47,48).
6. EuroQol EQ-5D-5L score ([EQ-5D-5L – EQ-5D \(euroqol.org\)](http://EQ-5D-5L - EQ-5D (euroqol.org))) (49)
7. Pittsburgh Sleep Problem Scale at 12 and 24-months post randomisation (32)
8. Return to Work/Employment Questionnaire (9,10).

9. Additional study-knee related operative intervention at 12 and 24-months post randomisation

10. Intraoperative and postoperative complications 12 and 24 months post-randomisation

11. Health Economic Evaluation Outcomes

- a. Health and social care resource utilisation and associated NHS and PSS cost and Quality Adjusted life years (QALY) at 24 months
- b. Incremental Cost per QALY at 24 months
- c. NHS and PSS cost, and QALYs as modelled over a lifetime horizon to account for future impacts on the need for TKR and associated revision surgery and their timing relative to retirement
- d. Incremental Cost per QALY as modelled over a lifetime horizon to account for future impacts on the need for TKR and associated revision surgery and their timing relative to retirement.

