7 DATA COLLECTION

The database and data management plan will be created, validated, and administered by the Edinburgh Clinical Trials Unit (ECTU), following Standard Operating Procedures. All data will be collected by those trained and delegated via the site delegation log. Follow ups at 12 and 24 month will be collected centrally by Edinburgh clinical Trials Unit (ECTU) via provision of an online portal or postal/emailed follow ups.

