However, the components of the non-surgical intervention are likely to be similar with each centre, and vary between centres, so clustering on centre within the non-surgical intervention arm is more appropriate. We have assumed that the intracluster correlation coefficient of the KOOS in the non-surgical intervention arm of each centre is 0.056. If there are 10 patients per centre, we get a design effect of 1.504. [design effect = $1+(0.056*(10-1)) = 1.504$]. We have adjusted for clustering in the physiotherapy arm through multiplying by the square root of the design effect (1.226) to obtain a standard deviation in the physiotherapy arm of 15.9. Using 90% power, 2-sided $p=0.05$, with a difference of 7.2, and standard deviations of 14.4 and 15.9, this gives a sample size of 95 per group. Allowing for 15% loss to follow up gives 112 per group.

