9.3 Health economic analyses

Health economic analysis will include two components:

1. A within trial analysis will profile the short-term patterns of health and social care resource utilisation and health impacts over the observable 24-month trial period, and examine relative short term cost-efficiency of each trial.
2. A long run cost-efficiency model, extrapolating changes patient outcomes over a lifetime horizon to account for future impacts on the need for TKR and associated revision, and their timing relative to retirement.

Full details of these analyses will be specified in a comprehensive Health Economic Analysis Plan, authored by the study health economist(s), and signed off by the PI prior to analysis, however the following section offers an overview:

To maximise UK policy relevance, health economic analysis will follow NICE reference case recommendations (53) including: The adoption of an NHS and PSS (personal social service) costing perspective for primary analyses; cost-utility approach (results presented in terms of incremental cost effectiveness ratios (ICERs) on a cost per quality adjusted life year (QALY) basis, with QALYs derived from EQ-5D-5L utility scores using NICE's preferred scoring algorithm at time of analysis); choice of discount rate (where applicable); and use of probabilistic sensitivity analysis (PSA). Secondary analysis will investigate the impact of treatment choice on employment status.

Several key items of health care resource utilisation (HCRU) for the first 24 months post randomisation will be collected retrospectively from medical records, namely: Inpatient admissions; A&E visits; ambulance trips; physiotherapy, and other outpatient visits. Additional top up self-report surveying will be undertaken alongside EQ-5D-5L and other PROMs at 12 and 24 months for: primary care, pain medications; employment status; and any HCRU not obtainable from medical records. HCRU will be combined with standard UK price weights (54) to estimate costs with a base year set to the latest financial year for which at least one study participant provides data.

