The within trial analysis (component 1) will describe rates of resource use, associated cost, and health utility scores/QALYs, will be presented contextually as summary statistics for each trial arm, with comparisons of total cost and QALYs undertaken Generalised Linear Modelling to account for anticipated skew (55) Incremental cost per QALY will be estimated by appropriate technique with preference given a recycled predictions approach (56) if data permits. The proportion of patients changing employment status will be examined using logistic regression.

Missing data will be imputed using appropriate techniques depending on degree of missingness, most likely multiple imputation by chained equations (which is considered gold standard in this area (57)). It is however worth noting that the most important cost factors relate to inpatient readmission and outpatient activity, will be obtained from medical records thus are not anticipated be prone to missingness.

Longer run cost-efficiency in terms of incremental cost per QALY will be examined by means of decision analytic simulation modelling (Component 2), This will extrapolate patient outcomes over a lifetime horizon to account for future impacts on the need for TKR and associated revision, and their timing relative to retirement since these often have significant impacts on employment potential and related. Initial scoping suggests this to be at least achievable Markov modelling, though as available data appear to be rich, more sophisticated options will be explored as needed. Initially reporting from the model will utilise the 24-month trial data, complimented with NJR and KOR data on longer term rates of TKR, revision TKR, and associated EQ-5D utility scores, a recent Cochrane review (12), topped up to date of analysis, and parameters extracted from a similar model (58). Additional, potentially non-systematic, targeted literature searches may be necessary for specific parameters if not available from these sources.

Uncertainty around both within trial and modelled ICERs will be presented using PSA with cost-effectiveness acceptability curves (CEAC) generated. Should the model prove inconclusive, value of information analysis will be undertaken to identify critical parameters which are driving overall uncertainty in decision criteria to inform follow up research potentially using the data linkage permissions obtained at consent.

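### Study-knee operations (endpoint 9) are scheduled only through remote follow-up contact; the 24-month medical-records extraction already planned in section 9.3 should be their main source

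*Protocol*

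**What the plan says.** **Endpoint.** Section 2.2 lists as the ninth secondary endpoint "Additional study-knee related operative intervention at 12 and 24-months post randomisation".

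**Route.** Section 6 has the 12- and 24-month follow-up done "with all study assessments at these time points undertaken remotely via email, post or telephone", and non-responders are chased "with a maximum of two reminders sent where required". In Table 2 the row "Additional operative intervention in study knee" is ticked only in the 12- and 24-month PROMS columns. Those columns are run by the trials unit by email, post or online portal. Medical-records review appears in Table 2 for screening and for the MRAV proforma, and endpoint 9 is not ticked in either place. Section 7 describes central collection "via provision of an online portal or postal/emailed follow ups".

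**A second source, for another purpose.** Section 9.3 says that key resource-use items "for the first 24 months post randomisation will be collected retrospectively from medical records, namely: Inpatient admissions", followed by A&E, ambulance, physiotherapy and other outpatient contacts. It adds that the main cost items, inpatient readmission and outpatient activity, "will be obtained from medical records thus are not anticipated be prone to missingness".

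**Missing data.** Section 9.1 states "Allowing for 15% loss to follow up gives 112 per group". Section 9.2 expects about 10% missing on the primary outcome, plans a complete-case analysis, and treats secondary outcomes by similar methods where the data allow.

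**The concern.** An operation on the knee is a hospital event. It leaves a record whether or not the patient answers a questionnaire. The protocol nevertheless schedules it as though it were a patient-reported score, so the operation rate rests on those who reply. The trial is open, and patients who have had further surgery may reply more or less often than the rest.

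The endpoint matters clinically, because section 1.1 gives avoiding or delaying knee replacement as an aim of HTO. Adverse-event reporting is not a reliable back-up. Section 10 leaves out events tied to the known risks of surgery and complications already covered by secondary outcomes, and section 1.2.1 lists conversion to knee replacement among the procedure's risks.

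The economic analysis will be reading hospital admissions over the same 24 months. If procedure and side are not captured at that point, no later analysis plan can recover them without going back to the notes.

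**Working it through.** **1. The plan's own figure.** Inputs from section 9.1: SDs 14.4 and 15.9, difference 7.2, two-sided 5% level, 90% power.

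- Normal formula: n = (14.4² + 15.9²)(1.960 + 1.282)² / 7.2² = 93.3, so 94 per group.
- With the noncentral t, power is 0.8993 at 94 and 0.9023 at 95, so 95 per group.
- Loss: 95 / 0.85 = 111.8, so 112 per group and 224 in all.

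Both stated figures reproduce.

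**2. Participants without a 24-month value.**

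| Basis | Per arm | Total |
|---|---|---|
| About 10% missing (9.2) | 112 × 0.10 = 11.2 | 224 × 0.10 = 22.4 |
| 15% loss allowance (9.1) | 112 × 0.15 = 16.8 | 224 × 0.15 = 33.6 |

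Both percentages were set for the KOOS. Applying them to endpoint 9 is an assumption, reasonable because Table 2 collects both at the same contacts.

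**3. What the unknown values could do.** Take an assumed 10 operations among 95 responders in an arm, which is 10.5%. With 17 unknown, the full-arm rate lies between 10/112 = 8.9% and 27/112 = 24.1%.

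**4. Bias if loss depends on surgery.** Let p be the true operation rate, L the overall loss, and r the ratio of loss in operated to loss in unoperated patients. Then:

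- loss in unoperated patients: l0 = L / (1 − p + p·r)
- loss in operated patients: l1 = r·l0
- observed rate: p(1 − l1) / (1 − L)

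With p = 0.20 (the section 9.1 crossover assumption, borrowed here as an operation rate):

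| r (assumed) | Observed, L = 15% | Observed, L = 10% |
|---|---|---|
| 0.5 | 21.6% | 21.0% |
| 1 | 20.0% | 20.0% |
| 1.5 | 18.7% | 19.2% |
| 2 | 17.6% | 18.5% |
| 3 | 16.0% | 17.5% |

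Worked case, r = 3 and L = 15%: l0 = 0.15/1.4 = 0.107, l1 = 0.321, observed = 0.20 × 0.679 / 0.85 = 0.160.

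The standard error at n = 95 is √(0.16/95) = 4.1 points, so the most extreme case shown is about one standard error. At 10% loss (n about 101) the same ratio gives about 0.6 of a standard error.

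**5. Precision.** If all 112 in an arm could be scored, the standard error would be √(0.16/112) = 3.8 points. That is the best case, since full withdrawals reduce the denominator.

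**The case against.** Several points on the other side stand.

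- **Section 9.3 does not name knee operations.** It lists admissions and outpatient contacts, without procedure or side, and does not say that everyone will be covered. That it would capture the same events is an inference, and day-case surgery or unrecorded side would break the match. The extraction therefore has to be specified before it can serve endpoint 9.
- **Table 2 is a summary.** A reader might infer from its silence that the 24-month records review is not planned at all. That does not follow: section 9.3 states a retrospective extraction, which needs no visit column, and Table 2 has no row for resource use or adverse events either.
- **Source documents, data management and analysis plans are held separately.** They may settle which source prevails. But the protocol fixes the route for this endpoint in three places, and an analysis plan cannot supply items that were never extracted.
- **The counts are upper figures.** The 15% may include participants who withdraw from all aspects of the trial (section 5.3), someone lost after month 12 keeps a 12-month answer, and section 6 allows telephone contact, so a missing KOOS need not mean a missing answer about surgery.
- **The CACE analysis is not tied to endpoint 9.** A reader might infer that it depends on this questionnaire. The protocol never says so. Crossover is already judged in the 9-month pilot, so some other route must exist, and it is not stated whether a first HTO in a PKT patient counts as an additional operation.

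None of this gives a 24-month value to a participant who does not respond.

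**Conclusion.** The point holds as a cheap improvement to one secondary endpoint. As scheduled, endpoint 9 would be unknown at 24 months for about 22 participants, and for at most about 34, while a source that the protocol itself expects to be nearly complete is read for another purpose. The complete-case sentence in section 9.2 concerns the scales; its extension to endpoint 9 rests on the statement that secondary outcomes follow similar methods.

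The size and direction of any bias are unknown. The figures from 21.6% to 16.0% depend on assumed loss ratios, on 15% loss and on the crossover rate standing in for the operation rate. They describe one arm and do not show a bias in the treatment comparison. It would also go too far to say that records would remove all missingness, because participants who withdraw access to their records stay unscored. The KOOS analysis and the sample size are not affected.

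**What to change.** State in section 6 and Table 2 that the 24-month medical-records extraction of section 9.3 also records any operation on the study knee, with date, side and type, and including day cases. Name it as the main source for endpoint 9 in all randomised participants who have not withdrawn access to their records. Keep the questionnaire as a supplement, chiefly to pick up operations done at other hospitals. Say whether a first HTO in a participant allocated to PKT counts towards endpoint 9; the same entry can then confirm late crossover for the CACE analysis.

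The cost is protocol and CRF wording and slightly more data entry at sites, since records are already to be read for resource use. It should be settled before the extraction form is fixed.

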7 DATA COLLECTION

The database and data management plan will be created, validated, and administered by the Edinburgh Clinical Trials Unit (ECTU), following Standard Operating Procedures. All data will be collected by those trained and delegated via the site delegation log. Follow ups at 12 and 24 month will be collected centrally by Edinburgh clinical Trials Unit (ECTU) via provision of an online portal or postal/emailed follow ups.

